4.6.2 Subject Discontinuation from the Study

Subjects have the right to voluntarily withdraw from the study at any time for any reason. In addition, the investigator has the right to withdraw a subject from the study at any time.

Entrectinib—Genentech, Inc.
38/Protocol GP41341, Version 1 – 02 April 2019

Reasons for subject discontinuation from the study may include, but are not limited to, the following:

- Subject withdrawal of consent
- Study termination or site closure
- Adverse event
- Loss to follow-up
- Subject non-compliance, defined as failure to comply with protocol requirements as determined by the investigator or Sponsor

Every effort should be made to obtain a reason for subject discontinuation from the study. The primary reason for discontinuation from the study should be documented on the appropriate eCRF. If a subject requests to be withdrawn from the study, this request must be documented in the source documents and signed by the investigator.

For a subject who withdraws because of an IMP-related adverse event, every effort will be made to ensure the subject completes follow-up procedures. Any subject withdrawn or discontinuing the study prematurely because of an IMP-related adverse event or termination of the study will be considered to have completed the study, and will not be replaced. Subjects who discontinue study treatment may be replaced at the discretion of the Sponsor and the investigator to ensure a minimum of 12 evaluable subjects in each study part.

A subject is considered evaluable if they have sufficient data to ensure the primary objective of the relevant study part is met.

4.6.3 Study Discontinuation

The Sponsor has the right to terminate this study at any time. Reasons for terminating the study may include, but are not limited to, the following:

- The incidence or severity of adverse events in this or other studies indicates a potential health hazard to subjects
- Subject enrollment is unsatisfactory

The Sponsor will notify the investigator if the Sponsor decides to discontinue the study.

After the start of protocol activities but prior to the commencement of dosing, the study may be terminated by the Sponsor and investigator without consultation with the MHRA and EC. The end of the trial must be notified to the MHRA and EC immediately and at the latest within 15 days after the study is terminated, clearly explaining the reasons. A description of follow up measures taken for safety reasons if applicable will also be provided.

Entrectinib—Genentech, Inc.
39/Protocol GP41341, Version 1 – 02 April 2019

If the study is abandoned prior to commencement of any protocol activities, the Principal Investigator or Sponsor must notify the EC and MHRA by letter outlining the reasons for abandonment of the trial.

If it becomes necessary to consider termination of the study after dosing has begun, dosing may be suspended pending discussion between the investigator and Sponsor. Dosing will be stopped immediately on safety grounds.

The study may be terminated or suspended at the request of the MHRA or EC.

4.6.4 Site Discontinuation

The Sponsor has the right to close a site at any time. Reasons for closing a site may include, but are not limited to, the following:

- Excessively slow recruitment
- Poor protocol adherence
- Inaccurate or incomplete data recording
- Non-compliance with the International Council for Harmonisation (ICH) guideline for Good Clinical Practice
- No study activity (i.e., all subjects have completed the study and all obligations have been fulfilled)

5. ASSESSMENT OF SAFETY

5.1 SAFETY PLAN

Entrectinib is not approved, and clinical development is ongoing. The safety plan for volunteers in this study is based on clinical experience with entrectinib in completed and ongoing studies. The anticipated important safety risks for entrectinib are described in the entrectinib IB.

Several measures will be taken to ensure the safety of subjects participating in this study. Eligibility criteria have been designed to exclude subjects at higher risk for toxicities. Subjects will undergo safety monitoring during the study, including assessment of the nature, frequency, and severity of adverse events.

5.2 SAFETY PARAMETERS AND DEFINITIONS

Safety assessments will consist of monitoring and recording adverse events, including serious adverse events and adverse events of special interest, performing protocol-specified safety laboratory assessments, measuring protocol-specified vital signs, and conducting other protocol-specified tests that are deemed critical to the safety evaluation of the study.

Certain types of events require immediate reporting to the Sponsor, as outlined in Section 5.4.

Entrectinib—Genentech, Inc.
40/Protocol GP41341, Version 1 – 02 April 2019

5.2.1 Adverse Events

According to the ICH guideline for Good Clinical Practice, an adverse event is any untoward medical occurrence in a clinical investigation subject administered a pharmaceutical product, regardless of causal attribution. An adverse event can therefore be any of the following:

- Any unfavorable and unintended sign (including an abnormal laboratory finding), symptom, or disease temporally associated with the use of a medicinal product, whether or not considered related to the medicinal product
- Any new disease or exacerbation of an existing disease (a worsening in the character, frequency, or severity of a known condition) (see Section [5.3.5.8](#) for more information)
- Recurrence of an intermittent medical condition (e.g., headache) not present at baseline
- Any deterioration in a laboratory value or other clinical test (e.g., ECG, X-ray) that is associated with symptoms or leads to a change in study treatment or concomitant treatment or discontinuation from study drug
- Adverse events that are related to a protocol-mandated intervention, including those that occur prior to assignment of study treatment (e.g., screening invasive procedures such as biopsies)

5.2.2 Serious Adverse Events (Immediately Reportable to the Sponsor)

A serious adverse event is any adverse event that meets any of the following criteria:

- Is fatal (i.e., the adverse event actually causes or leads to death)
- Is life threatening (i.e., the adverse event, in the view of the investigator, places the subject at immediate risk of death)
This does not include any adverse event that, had it occurred in a more severe form or was allowed to continue, might have caused death.
- Requires or prolongs subject hospitalization (see Section [5.3.5.9](#))
- Results in persistent or significant disability/incapacity (i.e., the adverse event results in substantial disruption of the subject's ability to conduct normal life functions)
- Is a congenital anomaly/birth defect in a neonate/infant born to a mother exposed to study drug
- Is a significant medical event in the investigator's judgment (e.g., may jeopardize the subject or may require medical/surgical intervention to prevent one of the outcomes listed above)

The terms "severe" and "serious" are not synonymous. Severity refers to the intensity of an adverse event (e.g., rated as mild, moderate, or severe, or according to National Cancer Institute Common Terminology Criteria for Adverse Events [NCI CTCAE]; see

Entrectinib—Genentech, Inc.
41/Protocol GP41341, Version 1 – 02 April 2019

Section 5.3.3); the event itself may be of relatively minor medical significance (such as severe headache without any further findings).

Severity and seriousness need to be independently assessed for each adverse event recorded on the eCRF.

Serious adverse events are required to be reported by the investigator to the Sponsor immediately (i.e., no more than 24 hours after learning of the event; see Section 5.4.2 for reporting instructions).

5.2.3 Adverse Events of Special Interest (Immediately Reportable to the Sponsor)

Adverse events of special interest are required to be reported by the investigator to the Sponsor immediately (i.e., no more than 24 hours after learning of the event; see Section 5.4.2 for reporting instructions). Adverse events of special interest for this study are as follows:

- All grades of syncope
- Congestive heart failure \geq Grade 2
- QT prolongation \geq Grade 2
- Cognitive disturbances \geq Grade 3
- Cases of potential drug-induced liver injury that include an elevated ALT or AST in combination with either an elevated bilirubin or clinical jaundice, as defined by Hy's Law (see Section 5.3.5.6)
- Suspected transmission of an infectious agent by the study drug, as defined below

Any organism, virus, or infectious particle (e.g., prion protein transmitting transmissible spongiform encephalopathy), pathogenic or non-pathogenic, is considered an infectious agent. A transmission of an infectious agent may be suspected from clinical symptoms or laboratory findings that indicate an infection in a subject exposed to a medicinal product. This term applies only when a contamination of the study drug is suspected.

5.3 METHODS AND TIMING FOR CAPTURING AND ASSESSING SAFETY PARAMETERS

The investigator is responsible for ensuring that all adverse events (see Section 5.2.1 for definition) are recorded on the Adverse Event eCRF and reported to the Sponsor in accordance with instructions provided in this section and in Sections 5.4–5.6.

For each adverse event recorded on the Adverse Event eCRF, the investigator will make an assessment of seriousness (see Section 5.2.2 for seriousness criteria), severity (see Section 5.3.3), and causality (see Section 5.3.4).

Entrectinib—Genentech, Inc.
42/Protocol GP41341, Version 1 – 02 April 2019

5.3.1 Adverse Event Reporting Period

Investigators will seek information on adverse events at each subject contact. All adverse events, whether reported by the subject or noted by study personnel, will be recorded in the subject's medical record and on the Adverse Event eCRF.

After informed consent has been obtained but prior to initiation of study drug, only serious adverse events caused by a protocol-mandated intervention (e.g., invasive procedures such as biopsies, discontinuation of medications) should be reported (see Section [5.4.2](#) for instructions for reporting serious adverse events).

After initiation of study drug, all adverse events will be reported until the Follow-up phone call (12 to 14 days after the final dose of study drug).

Instructions for reporting adverse events that occur after the adverse event reporting period are provided in Section [5.6](#).

5.3.2 Eliciting Adverse Event Information

A consistent methodology of non-directive questioning should be adopted for eliciting adverse event information at all subject evaluation time points. Examples of non-directive questions include the following:

"How have you felt since your last clinic visit?"

"Have you had any new or changed health problems since you were last here?"

5.3.3 Assessment of Severity of Adverse Events

The adverse event severity grading scale for the NCI CTCAE (v5.0) will be used for assessing adverse event severity. [Table 3](#) will be used for assessing severity for adverse events that are not specifically listed in the NCI CTCAE.

Table 3 Adverse Event Severity Grading Scale for Events Not Specifically Listed in NCI CTCAE

Grade	Severity
1	Mild; asymptomatic or mild symptoms; clinical or diagnostic observations only; or intervention not indicated
2	Moderate; minimal, local, or non-invasive intervention indicated; or limiting age-appropriate instrumental activities of daily living ^a
3	Severe or medically significant, but not immediately life threatening; hospitalization or prolongation of hospitalization indicated; disabling; or limiting self-care activities of daily living ^{b, c}
4	Life-threatening consequences or urgent intervention indicated ^d
5	Death related to adverse event ^d

Note: Based on the most recent version of NCI CTCAE (v5.0), which can be found at: http://ctep.cancer.gov/protocolDevelopment/electronic_applications/ctc.htm

- ^a Instrumental activities of daily living refer to preparing meals, shopping for groceries or clothes, using the telephone, managing money, etc.
- ^b Examples of self-care activities of daily living include bathing, dressing and undressing, feeding oneself, using the toilet, and taking medications, as performed by subjects who are not bedridden.
- ^c If an event is assessed as a "significant medical event," it must be reported as a serious adverse event (see Section 5.4.2 for reporting instructions), per the definition of serious adverse event in Section 5.2.2.
- ^d Grade 4 and 5 events must be reported as serious adverse events (see Section 5.4.2 for reporting instructions), per the definition of serious adverse events in Section 5.2.2.

5.3.4 Assessment of Causality of Adverse Events

Investigators should use their knowledge of the subject, the circumstances surrounding the event, and an evaluation of any potential alternative causes to determine whether an adverse event is considered to be related to the study drug, indicating "yes" or "no" accordingly. The following guidance should be taken into consideration (see also Table 4):

- Temporal relationship of event onset to the initiation of study drug
- Course of the event, with special consideration of the effects of dose reduction, discontinuation of study drug, or reintroduction of study drug (as applicable)
- Known association of the event with the study drug or with similar treatments
- Known association of the event with the disease under study
- Presence of risk factors in the subject or use of concomitant medications known to increase the occurrence of the event
- Presence of non-treatment-related factors that are known to be associated with the occurrence of the event

Entrectinib—Genentech, Inc.
44/Protocol GP41341, Version 1 – 02 April 2019

Table 4 Causal Attribution Guidance

Is the adverse event suspected to be caused by the study drug on the basis of facts, evidence, science-based rationales, and clinical judgment?	
YES	There is a plausible temporal relationship between the onset of the adverse event and administration of the study drug, and the adverse event cannot be readily explained by the subject's clinical state, intercurrent illness, or concomitant therapies; and/or the adverse event follows a known pattern of response to the study drug; and/or the adverse event abates or resolves upon discontinuation of the study drug or dose reduction and, if applicable, reappears upon re-challenge.
NO	An adverse event will be considered related, unless it fulfills the criteria specified below. Evidence exists that the adverse event has an etiology other than the study drug (e.g., preexisting medical condition, underlying disease, intercurrent illness, or concomitant medication); and/or the adverse event has no plausible temporal relationship to administration of the study drug (e.g., cancer diagnosed 2 days after first dose of study drug).

5.3.5 Procedures for Recording Adverse Events

Investigators should use correct medical terminology/concepts when recording adverse events on the Adverse Event eCRF. Avoid colloquialisms and abbreviations.

Only one adverse event term should be recorded in the event field on the Adverse Event eCRF.

5.3.5.1 Diagnosis versus Signs and Symptoms

A diagnosis (if known) should be recorded on the Adverse Event eCRF rather than individual signs and symptoms (e.g., record only liver failure or hepatitis rather than jaundice, asterixis, and elevated transaminases). However, if a constellation of signs and/or symptoms cannot be medically characterized as a single diagnosis or syndrome at the time of reporting, each individual event should be recorded on the Adverse Event eCRF. If a diagnosis is subsequently established, all previously reported adverse events based on signs and symptoms should be nullified and replaced by one adverse event report based on the single diagnosis, with a starting date that corresponds to the starting date of the first symptom of the eventual diagnosis.

5.3.5.2 Adverse Events That Are Secondary to Other Events

In general, adverse events that are secondary to other events (e.g., cascade events or clinical sequelae) should be identified by their primary cause, with the exception of severe or serious secondary events. A medically significant secondary adverse event that is separated in time from the initiating event should be recorded as an independent event on the Adverse Event eCRF. For example:

- If vomiting results in mild dehydration with no additional treatment in a healthy adult, only vomiting should be reported on the eCRF.
- If vomiting results in severe dehydration, both events should be reported separately on the eCRF.

Entrectinib—Genentech, Inc.
45/Protocol GP41341, Version 1 – 02 April 2019

- If a severe gastrointestinal hemorrhage leads to renal failure, both events should be reported separately on the eCRF.
- If dizziness leads to a fall and consequent fracture, all three events should be reported separately on the eCRF.
- If neutropenia is accompanied by an infection, both events should be reported separately on the eCRF.

All adverse events should be recorded separately on the Adverse Event eCRF if it is unclear as to whether the events are associated.

5.3.5.3 Persistent or Recurrent Adverse Events

A persistent adverse event is one that extends continuously, without resolution, between subject evaluation time points. Such events should only be recorded once on the Adverse Event eCRF. The initial severity (intensity or grade) of the event will be recorded at the time the event is first reported. If a persistent adverse event becomes more severe, the most extreme severity should also be recorded on the Adverse Event eCRF. If the event becomes serious, it should be reported to the Sponsor immediately (i.e., no more than 24 hours after learning that the event became serious; see Section 5.4.2 for reporting instructions). The Adverse Event eCRF should be updated by changing the event from "non-serious" to "serious," providing the date that the event became serious, and completing all data fields related to serious adverse events.

A recurrent adverse event is one that resolves between subject evaluation time points and subsequently recurs. Each recurrence of an adverse event should be recorded as a separate event on the Adverse Event eCRF.

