10.3 Adverse Events

An AE is any untoward medical occurrence in a clinical investigation subject administered a pharmaceutical product, regardless of causal attribution.

Throughout the study, all AEs will be evaluated by the PI and noted in the AE section of the eCRF. AEs will be monitored from the time the subject signs the informed consent form (ICF) until after the final follow-up call in each period and each study part.

AEs will be coded using MedDRA v22.0 (or most recent version) and reported by SOC and PT.

AEs will be classified into the following categories:

- pre-dose AEs: AEs recorded after informed consent has been obtained and prior to the first dose of IMP. Only Serious Adverse Events (SAEs) caused by protocol mandated intervention (e.g., invasive procedures such as biopsies, discontinuation of medications) will be reported
- treatment-emergent adverse events (TEAEs): AEs that commence during/after the first dose of IMP or commence before first dose of IMP (i.e., a pre-dose AE or existing medical condition) but worsen in intensity during exposure to IMP

Where the severity of a pre-dose AE intensifies during/after dosing this will be defined as a new AE and classified as a TEAE.

TEAEs will be assigned to the treatment of the period in which the AE first occurred. Where the severity of an AE intensifies or symptoms change in a subsequent period, this

will be defined as a new AE and included under the treatment associated with the subsequent period. AEs that occur during the washout period will be assigned to the treatment the subject received during the period immediately before the washout period.

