An IMP-related AE is any AE where a causal relationship with the IMP is at least a reasonable possibility. When considering their relationship to IMP, AEs will be classified as "YES" (i.e., there is a plausible temporal relationship between the onset of the adverse event and administration of the study drug, and the adverse event cannot be readily explained by the subject's clinical state, intercurrent illness, or concomitant therapies; and/or the adverse event follows a known pattern of response to the study drug; and/or the adverse event abates or resolves upon discontinuation of the study drug or dose reduction and, if applicable, reappears upon re-challenge.) or "NO" (i.e., evidence exists that the adverse event has an etiology other than the study drug [e.g., pre-existing medical condition, underlying disease, intercurrent illness, or concomitant medication]; and/or the adverse event has no plausible temporal relationship to administration of the study drug [e.g., cancer diagnosed 2 days after first dose of study drug]). Pre-dose AEs will always have the classification of "NO" when considering their relationship to IMP.

The severity of AEs will be assessed according to the National Cancer Institute Common Terminology Criteria for Adverse Events (NCI CTCAE, v5.0) grading scale when considering their initial and maximum severity separately. All summary tables will be based on maximum severity but relevant listings will include both initial and maximum severity:

Grade	Severity
1	Mild; asymptomatic or mild symptoms; clinical or diagnostic observations only; or intervention not indicated
2	Moderate; minimal, local, or non-invasive intervention indicated; or limiting age-appropriate instrumental activities of daily living ^a
3	Severe or medically significant, but not immediately life threatening; hospitalization or prolongation of hospitalization indicated; disabling; or limiting self-care activities of daily living ^{b, c}
4	Life-threatening consequences or urgent intervention indicated ^d
5	Death related to AE ^d

^a Instrumental activities of daily living refer to preparing meals, shopping for groceries or clothes, using the telephone, managing money, etc.

^b Examples of self-care activities of daily living include bathing, dressing and undressing, feeding oneself, using the toilet, and taking medications, as performed by subjects who are not bedridden.

^c If an event is assessed as a "significant medical event," it must be reported as a serious AE.

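### A persistent adverse event is kept as one record with no date of worsening, so SAP 10.3 cannot reliably move a non-serious Grade 1-to-2 worsening or a symptom change to the later formulation

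*Protocol*

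**What the plan says.** Protocol 5.3.5.3 sets the recording rule for the site. It defines the case: "A persistent adverse event is one that extends continuously, without resolution, between subject evaluation time points". It then states: "Such events should only be recorded once on the Adverse Event eCRF". On severity it says: "The initial severity (intensity or grade) of the event will be recorded at the time the event is first reported"; and "If a persistent adverse event becomes more severe, the most extreme severity should also be recorded on the Adverse Event eCRF". The one change it asks the site to date is a change to serious, by "providing the date that the event became serious, and completing all data fields related to serious adverse events". It makes no exception for a subject who has crossed to another formulation. Protocol 5.3.5.4 and 5.3.5.5 repeat the record-once rule for laboratory and vital-sign abnormalities.

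SAP 10.3 sets the attribution rule. The general rule is: "TEAEs will be assigned to the treatment of the period in which the AE first occurred". An exception follows. "Where the severity of an AE intensifies or symptoms change in a subsequent period", the SAP treats it as a new event and counts it under the treatment of that later period. On severity: "All summary tables will be based on maximum severity but relevant listings will include both initial and maximum severity".

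Neither document says how one protocol record becomes the two events that the SAP exception requires. SAP 13.2 declares no change to the planned analysis.

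**The concern.** In a crossover, an event still open at the next dose belongs to two treatments in turn. The SAP recognises this and has a rule for it. To apply that rule, the data must show either a second record or the date on which the grade or symptoms changed. The protocol asks for neither unless the event becomes serious.

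The incidence and severity of adverse events is one of the secondary endpoints (Protocol 2.2), and SAP section 10 presents safety data by actual treatment. If the change cannot be dated, what remains is the period of onset and the maximum grade. Together these can charge the worse grade to the formulation given first and leave the later formulation with no event. Causality has the same problem, since one record does not hold separate judgements for two formulations.

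**Working it through.** The plan states no figure to reproduce. The check sets the two rules side by side, traces one event through both, and sizes the effect.

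**1. What the single record can show.** Take a non-serious event with onset in Period 1, initial Grade 1, maximum Grade 2, still ongoing in a later period. The fields described in Protocol 5.3.5.3 read the same whether the grade rose in Period 1, 2 or 3: onset Period 1, initial 1, maximum 2. The SAP exception separates these cases, but the record does not.

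**2. One event under both rules.** Onset at Grade 1 in Period 1 on T1; continuous; Grade 2 after the Period 2 dose of T2.

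| | T1 | T2 |
|---|---|---|
| SAP 10.3 exception applied | Grade 1 | Grade 2 |
| Single record, first-occurrence rule, maximum severity | Grade 2 | no event |

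The T1 subject moves from the Grade 1 cell to the Grade 2 cell. T2 loses one subject from its Grade 2 cell and from its any-TEAE row. For a change of symptoms without a change of grade, T2 loses one subject from the any-TEAE row.

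**3. Which grades are affected.**
- *Severe (Grade 3), non-serious.* Protocol 4.6.1 gives no further study treatment to a subject who has had a serious or severe adverse event. A subject who received a later dose therefore had not reached Grade 3 before it, absent a deviation. The Grade 3 maximum must follow the last dose received, and dosing dates are listed (SAP 10.1).
- *Serious, including Grades 4 and 5.* Grades 4 and 5 must be reported as serious (Protocol 5.3.3, Table 3), and the date of becoming serious is recorded.
- *Recurrent events.* An event that resolves and returns gets its own record under Protocol 5.3.5.3.
- *What is left.* Non-serious worsening from Grade 1 to Grade 2, and changes of symptoms.

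**4. Size per affected subject.** The denominators at planned enrolment are 15 in Part 1 and 16 in Part 2 (Protocol 4.1).
- Part 1: 1/15 = 6.7 percentage points in a cell.
- Part 2: 1/16 = 6.25 percentage points.
- If only 12 subjects contribute to a treatment: 1/12 = 8.3 percentage points.

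**5. Reach.** The event must still be open at the next dose. Doses are at least 14 days apart: 14 × 24 = 336 h. With the terminal half-life of about 20 to 30 h (Protocol 1.1.2.2), that is 336/30 = 11.2 to 336/20 = 16.8 half-lives. Few drug-related events are likely to last that long and then worsen. The documents give no rate, so no expected count can be calculated.

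**The case against.** The strongest reply is that the two texts work at different levels. The protocol tells the site how to fill in a form; the SAP defines how events are counted. Site queries can connect the two. The eCRF and its guidance are not among the documents, so a field for the date of a severity change may exist. The SAP calls its mock outputs illustrative, so the absence of such a date from the mock adverse event listing proves little. Adverse events are also kept in the medical record, and laboratory, vital-sign and ECG values are listed separately by period and time point. Lastly, the SAP never says that undated worsening reverts to the first period.

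Much of this stands. It limits the point to the fields the documents describe, and it means that misplacement under the earlier formulation can happen rather than must happen. It does not remove the conflict. No section asks for the date or the second record, or tells the programmer what to do without them. Measured values help only where the event is itself an abnormal measurement.

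A reader might infer more: that a mild event on one formulation that becomes severe after the next would be tabulated as severe on the first, shifting the severe row. The documents do not support that, because the discontinuation rule in Protocol 4.6.1 and the dated change to serious allow those events to be placed. Nor do they support a claim that a planned between-formulation comparison is distorted: the adverse event tables are descriptive (SAP 10.3.1), and no such comparison is planned.

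**Conclusion.** The inconsistency is real and narrow. For a non-serious event that starts in one period and goes from Grade 1 to Grade 2, or changes symptoms, after a later dose, a site that follows the protocol does not supply what the SAP rule needs. The worse grade can then appear under the earlier formulation. Each affected subject moves a Grade 2 or any-TEAE cell by about 6.7 points in Part 1 or 6.25 points in Part 2. Few such events are expected, and the primary pharmacokinetic endpoint is not touched.

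This rests on three assumptions: the eCRF holds no date of severity or symptom change beyond what the documents describe; full planned enrolment supplies the denominators; and subjects are handled as Protocol 4.6.1 states after a severe or serious event. If the eCRF already dates each change, only an alignment of wording remains.

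**What to change.** Align Protocol 5.3.5.3 and the eCRF completion guidance with SAP 10.3 in one of two ways:

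- When an event that is ongoing at a later period's dose worsens or changes in character after that dose, close the record at the date and time of change. Open a new linked record with its own onset, grade and causality.
- Keep one record, but capture the date and time of each change of severity or symptoms.

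The first option lets SAP 10.3 be applied as written and also gives a separate causality judgement for each formulation. It costs one sentence of guidance and a slightly higher event count. The number of distinct subjects with an event does not change, although the later formulation gains the subject that the SAP rule intends it to have. The second option costs one extra eCRF field.

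If neither can be made before data are collected, SAP 10.3 should state how undated worsening is assigned, and affected records should be queried with the site. The adverse event listing should in any case show initial and maximum severity, as SAP 10.3 promises; the mock listing has a single severity entry.
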